We plan to conduct a randomized double-blinded study investigating the role of DigiFab in patients with elevated risk of acute kidney injury undergoing CABG surgery. Patients who are undergoing CABG, meet the inclusion criteria, and provide consent will be enrolled in this study and randomized to either DigiFab arm or the placebo (vehicle) arm. The number of patients to be consented will be enough to achieve two hundred and fifty evaluable participants. The number consented will not be more than 350 patients. The study involves a follow up period of 72 hours post CABG surgery.

3A- Recruitment

All patients awaiting non-emergency CABG surgery will be considered for this study. Patients with high risk of developing AKI post CABG will be included in this study. High risk of AKI will be defined as one of the following: GFR >15 but below 60 (must be >36 hours after receiving any contrast, but within two weeks of signing consent) or a history of diabetes mellitus. Diabetes will be defined as a past diagnosis or a current hemoglobin a1c of \geq 6.5%.

3B. Inclusion Criteria

Each patient must meet all the following criteria to be enrolled in this study:

- Patient provided informed consent
- Male or female > 18 years of age
- Undergoing CABG and one of the following:
 - GFR (Cockcroft-Gault) less than 60 (should be > 36 hours after receiving any contrast, but within two weeks of signing consent)
 - o Past diagnosis of Diabetes or current Hemoglobin A1c of \geq 6.5%

3C . Exclusion criteria

A patient who meets any of the following criteria will be excluded from this study:

- AKI defined as:
 - o Decrease in GFR > 25% of baseline based on RIFLE criteria¹⁷
- Received contrast within the past 36 hours of IP administration
- Prior kidney transplantation
- Prior adverse reaction to DigiFab
- Received Digoxin within the past 30 days

- Has allergy to papaya, papain, or sheep proteins
- GFR < 15 (within two weeks of signing consent and > 36 hours after receiving contrast)

Calculation of Creatinine Clearance (Ccr; Cockcroft-Gault Formula)

 $C_{Cr} = \{((140 - age) \times weight)/(72xS_{Cr})\} \times 0.85 \text{ (if female)}\}$

 C_{Cr} (creatinine clearance) = mL/minute

Age = years; Weight = kg

SCr (serum creatinine) = mg/dL

3D. Enrollment and Baseline

Patients awaiting surgery in the hospital or having elective surgery and initially seen as outpatients will be eligible for this study.

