After a participant completes the consent process and is deemed eligible for this study, baseline parameters will be obtained. Laboratory tests—including basic metabolic panel (BMP, including serum creatinine), NT-pro-BNP (N-terminal prohormone of brain natriuretic peptide), and troponin—and hemodynamics – heart rate, blood pressure (systolic, diastolic, and mean arterial pressure)—obtained ideally within 24 hours before IP administration will be recorded. If multiple values exist within this time frame, the value closest to time of surgery will be used. Blood for EO concentrations, Proenkephalin A,¹⁸ and TIMP × IGFBP7^{19,20,21} will be drawn prior to investigational drug administration. Patient characteristics including age, sex, comorbidities (hypertension and diabetes) will be noted. Of note, ouabain concentrations take many days to return and will not be known prior to CABG.,

3E. Randomization

After ensuring eligibility, patients will be randomized by the investigational pharmacy. Stratified randomization will be employed using race and sex. Patients will be randomized approximately 24 hours prior to surgery. In the event that surgery is postponed to a later date, patients will be permitted to remain in the study. Digifab will be re-administered according to the usual protocol. If surgery is moved a second time and Digifab had been given, patients will be removed from the study.

3F. Intervention

BTG will provide DigiFab; placebo (saline) will be provided by the pharmacy. In-hospital study patients will be dosed intravenously with 80 mg Digifab or an equivalent volume of fluid the night prior to surgery (approximately 12-15 hours prior to surgery) and again 1 hour preoperatively. The vials will be stored in the hospital investigational pharmacy. Patients being admitted to the hospital on the day of surgery will receive 80 mg Digifab or an equivalent volume of fluid approximately 1 hour prior to surgery.

3G. Post-operative data:

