We will collect blood for endogenous ouabain, Proenkephalin A, and TIMP × IGFBP7 in the immediate post-operative period 0 to 4 hours post-surgery. The ouabain measurement at this time will determine the fraction that is free and that which is bound to DigiFab. This 4 hr post-op sample window provides the only opportunity to obtain critical information concerning the efficacy of the DigiFab immunoneutralization. Total serum ouabain, Proenkephalin A, TIMP × IGFBP7, and creatinine concentrations will also be obtained at 72 +/- 12 hours post-surgery.

Time spent on cardiopulmonary bypass will be noted. Seven days post-operatively, need for any type of renal replacement therapy will be recorded. Lastly, mortality within a seven-day period will be noted.

3H. Data collection

Each variable will be captured and stored in a HIPAA compliant and secure database.

31. Primary endpoint: Changes in GFR will be compared in patients who receive placebo and intervention by ANOVA and, as appropriate, parametric or non-parametric tests. The primary endpoint will compare only patients with the 50% highest baseline (preoperative) concentrations of ouabain.

3J. Secondary endpoints:

- 1. Comparing GFR amongst all patients
- 2. Incidence of AKI comparing the groups (25% decrease from baseline)
- 3. Incidence of renal replacement therapy by 30 days
- 4. Comparing intraoperative and 30 day mortality for placebo vs DigiFab.
- 5. In patients on cardiopulmonary bypass for the longest time (top 50%).
- 6. Comparison of change in Proenkephalin A in patients receiving Digifab and placebo.
- 7. Comparison of change of TIMP × IGFBP7 in patients receiving Digifab and placebo.
- 8. Comparison of GFR in patients receiving one dose and patients receiving two doses of Digifab.

3K. Analysis

Mean comparisons will be made by ANCOVA and, as appropriate, parametric or non-parametric tests. Chi square will be used as indicated. We will control for GFR and sex.

3L. Power

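### Section 3K promises control for GFR and sex but names only chi-square for categorical outcomes, so no stated method delivers that control for AKI incidence, and the stratification factor race is left out

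*Combined protocol and SAP*

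**What the plan says.** Section 3K is the whole analysis section and has three sentences. For continuous outcomes: "Mean comparisons will be made by ANCOVA and, as appropriate, parametric or non-parametric tests". For categorical outcomes: "Chi square will be used as indicated". Then a general statement: "We will control for GFR and sex".

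Section 3J lists three binary secondary endpoints: AKI incidence (a 25% fall from baseline), renal replacement therapy by 30 days, and mortality. None has a test attached.

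Section 3E says "Stratified randomization will be employed using race and sex". Section 3D provides the covariates. Serum creatinine is part of the baseline laboratory tests, and "Patient characteristics including age, sex, comorbidities (hypertension and diabetes) will be noted". Race must be known before a patient can be randomised.

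On size, section 3 says "The number of patients to be consented will be enough to achieve two hundred and fifty evaluable participants".

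**The concern.** For means, ANCOVA can carry the promised control for GFR and sex. For binary outcomes the only named method is chi-square, and its ordinary form compares two proportions with no place for a covariate. The promise and the named tool do not fit together. The control list also holds one of the two randomisation strata (sex) and not the other (race), without a reason.

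AKI incidence is formally secondary, but it is the outcome in the hypothesis at the end of section 2 (Rationale) and in the trial's title. Reduced GFR is one of the two high-risk entry routes in 3A and one of only two covariates chosen for control, so the plan itself treats it as relevant to outcome. Two things are at stake: some power on that endpoint, and a choice of method left open until after the data are seen.

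**Working it through.** **The plan's own power figure.** Section 3L gives power above 70% for 62 per group, a difference of 36 µmol/l and SD 76. The standard error is 76 × √(2/62) = 13.65, and 36 / 13.65 = 2.64. Power is Φ(2.64 − 1.96) = 75% (two-sided 0.05, assumed because no alpha is stated). The figure reproduces, but it concerns creatinine. The documents give no power for AKI incidence, so what follows is illustrative.

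**Inputs for AKI.**
- From the documents: 250 evaluable participants; AKI in up to 30% of CABG patients (section 1).
- Assumed: 1:1 allocation (125 per arm), two-sided 0.05, 30% female, the treatment effect, and the prognostic strength of GFR and sex.

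**Closed-form anchor, no covariate.** Take 30% against 15%.
- Pooled proportion: 0.225. Null standard error: √(2 × 0.225 × 0.775 / 125) = 0.0528.
- Alternative standard error: √((0.21 + 0.1275) / 125) = 0.0520.
- Power: Φ((0.15 − 1.96 × 0.0528) / 0.0520) = 81%.

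**Simulation A: marginal rates fixed at 30% and 15%.** 4,000 trials per row. Logistic regression adjusts for GFR and sex. Mantel-Haenszel is stratified by sex and by GFR split at the median.

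| OR per SD of GFR / OR for sex | Chi-square | Logistic | Mantel-Haenszel | Logistic minus chi-square |
|---|---|---|---|---|
| 1.0 / 1.0 | 81.1% | 80.7% | 80.6% | −0.4 |
| 1.5 / 1.3 | 82.3% | 83.2% | 82.7% | 0.9 |
| 2.0 / 1.5 | 80.5% | 83.3% | 82.1% | 2.9 |
| 3.0 / 1.5 | 82.3% | 88.2% | 86.4% | 5.9 |

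With no treatment effect, rejection rates were 4.3% to 5.4% for all three methods.

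**Simulation B: conditional treatment log odds ratio fixed at −0.75.** Control AKI 30%, sex log odds 0.4, 4,000 trials per row.

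| GFR log odds per SD (OR) | Chi-square | Logistic | Gain |
|---|---|---|---|
| 0.5 (1.65) | 65% | 67% | 2 |
| 0.69 (2.0) | 62% | 66% | 4 |
| 1.0 (2.72) | 57% | 63% | 6 |
| 1.5 (4.48) | 46% | 58% | 12 |

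A variant with control AKI 27.5% gave gains of 0.2, 1.8, 1.6, 3.1, 5.9 and 11.6 points at odds ratios of 1.28, 1.5, 1.65, 2.0, 2.72 and 4.48. Other runs gave 8 points at about 2.7. Repeat runs can differ by a point or two: each power estimate has a Monte Carlo standard error of about √(0.65 × 0.35 / 4000) = 0.75 points.

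A and B differ in what is held constant. In B the marginal effect shrinks as the covariate strengthens, so chi-square power falls. In A it does not.

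**Cost of leaving the method open.** Ordinary chi-square, stratified Mantel-Haenszel and adjusted logistic regression all fit the wording of 3K. With GFR log odds of 0.41 to 1.1 per SD, the three disagreed on significance in 7% to 17% of trials with a true effect. If the most favourable were chosen afterwards, type I error rose from about 5% to between 6% and 8%.

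**Rare events.** The exact type I error of the uncorrected chi-square at event rates of 1%, 2% and 3% is 2.2%, 4.5% and 4.4%, so it is not inflated.

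**The case against.** Several stronger readings are tempting, and the documents do not support them.

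- *The plan tests AKI by chi-square and ignores covariates.* Section 3K names no endpoint and no version of the test, and its next sentence promises control. Chi-square for AKI is a fair inference, since no other categorical method is named, but it is an inference. The gap is that the plan does not say how the control is done.
- *Chi-square cannot adjust.* This is true of the ordinary test. A stratified Mantel-Haenszel chi-square can control for sex and banded GFR. Section 3K does not name it.
- *The result would be invalid.* Under randomisation the unadjusted comparison is valid, and the simulated type I error was near 5% throughout.
- *The loss is large.* Losses of 10 to 13 points need an odds ratio of about 4.5 per SD, which means baseline GFR alone reaching an AUC of about 0.82. Nothing in the documents suggests that. AKI is defined relative to each patient's own baseline, and patients with diabetes enter with no upper GFR limit.
- *Sparse endpoints need Fisher's exact test.* Fisher's test has no covariates either, and chi-square is not inflated at low event rates here.
- *This decides the trial.* The primary endpoint is change in GFR in the upper ouabain half, and for means 3K already names ANCOVA.

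Together these limit the point to specification and efficiency on a secondary endpoint. They do not supply the missing method, and they do not explain why race is absent.

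**Conclusion.** The point holds as a mismatch between what 3K promises and what it names. No stated method delivers control for GFR and sex on AKI incidence, no adjusted effect measure is given, and one of the two stratification factors is left out. The issue is efficiency and pre-specification, not bias.

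The likely power loss is about 0 to 4 points for a GFR odds ratio up to 2 per SD, and about 6 to 8 points at 2.7 per SD. This rests on 125 per arm, two-sided 0.05, control AKI of about 30%, a treatment effect near a halving of risk, and assumed covariate strengths. Race was not in the simulations, so what it adds is not quantified. The point is minor to moderate, and worth making because the remedy costs almost nothing.

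**What to change.** In 3K, state that AKI incidence will be analysed by logistic regression on arm, baseline GFR (continuous), sex and race, reporting a standardised risk difference with 95% CI, with unadjusted chi-square as a supporting analysis.

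For renal replacement therapy and death, where events are few, keep chi-square or use a Mantel-Haenszel test stratified by sex. Add that full control for GFR is not intended for these two endpoints, so that the general control sentence is not left contradicted.

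Add race to the control list, or say why it is omitted.

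The cost is a few sentences in 3K, written before unblinding. Creatinine and sex are already recorded, and race is known from randomisation. No new data, visits or participants are needed.

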Pre-operative treatment with DigiFab to prevent post-operative acute kidney injury (AKI) in patients at high risk for AKI undergoing cardiac bypass graft surgery

April 24, 2022

NCT # HP-00083553

1. Introduction

Acute kidney injury (AKI) occurs in up to 30% of patients undergoing coronary artery bypass graft (CABG) surgery¹; consequently, renal replacement therapy is often required. In patients needing renal replacement therapy, mortality is as high as 60-70%². There has been a trend to operate on higher risk patients³, likely increasing the prevalence of AKI post CABG. With roughly four hundred thousand CABG surgeries performed annually in the US⁴, this represents an enormous health care problem. Currently, there is no known therapy for AKI or way to prevent AKI occurrence in this patient population. Evidence suggests that elevated preoperative circulating endogenous ouabain (EO), a cardiac glycoside structurally similar to digoxin, leads to increased risk of AKI post CABG^{5,6}. We propose to study the impact of giving preoperative DigiFab, a biological preparation approved by the FDA for the treatment of digitalis toxicity, as a means to reduce/prevent the incidence of CABG-evoked AKI. DigiFab is expected to have a beneficial and possibly unique utility in this scenario because the antibodies it contains have the side-property of also binding EO with high affinity ([name] & [name], unpublished).

2. Rationale

Postoperative AKI is one of the most clinically significant causes of morbidity and mortality in patients undergoing CABG.³ Even minimal increases in serum creatinine are associated with increased mortality⁷. Similarly, acute renal failure is the strongest risk factor for death in patients undergoing cardiac surgery⁸. Clinical studies indicate that high pre-op plasma EO concentrations

are a marker for AKI in patients undergoing CABG surgery, and the highest plasma EO concentrations are associated with the highest risk and poorest clinical outcomes^{5,6}.

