We postulate that the average patient will have a GFR of 50 which correlates to a creatinine of 129 μ mol/l. Previous studies have shown a post-operative mean increase of 48 μ mol/l with a standard deviation of 76. Therefore, on average, post-operative creatinine should be 177 μ mol/l, which is roughly a GFR of 35. A trial of 62 patients per group (top half of elevated ouabain concentrations) should have a power of >70% to detect a 36 μ mol/l difference in plasma creatinine, i.e., a creatinine of 141 μ mol/l (177-36). A creatinine of 141 μ mol/l correlates to a GFR of 45—a ~25% increase in GFR.

4. Risks

The primary risk associated with this study includes all of the potential adverse effects of DigiFab including: anaphylactic and anaphylactoid reactions, delayed allergic reactions, and a febrile response to immune complexes formed. However, since the Fab fragment of the antibody lacks the antigenic determinants of the Fc region, this should pose a reduced immunogenic threat. Of note, no patients during the clinical trials experienced an anaphylactic event. Patients with allergies to sheep protein would be at particular risk. In a registry of 717 adult patients receiving DigiFab, 6 had a probable or possible adverse reaction to the medication. All were symptomatically treated successfully²². Study participants will be monitored closely for potential adverse effects in the perioperative, operative, and post-operative setting. If an anaphylactic

reaction occurs, epinephrine, steroids, an H2 blocker, and diphenhydramine will be given as appropriate. Each blood draw carries the risk of pain associated with the venous puncture. As this is the first use of DigiFab in this patient population, unknown side effects are possible.

Data Safety and Monitoring Board

There will be an independent Data Safety and Monitoring Board (DSMB) which will assess the safety of the trial after 62 patients (first 25% of patients are enrolled). An unblinded coordinator will provide the board with all adverse events and deaths to investigate. The DSM board will evaluate the cause of deaths and allergic reactions. The panel will consist of [name], [name], [name], and a statistician.

5. Benefits

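### Neither statement of the primary GFR analysis (ANOVA in 3I, ANCOVA in 3K) adjusts for baseline ouabain, so the plan forgoes a small, nearly free gain in precision

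*Combined protocol and SAP*

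**What the plan says.** Section 3I defines the primary comparison: "Changes in GFR will be compared in patients who receive placebo and intervention by ANOVA", with parametric or non-parametric tests where suitable. No covariate is mentioned. It then limits the population: "The primary endpoint will compare only patients with the 50% highest baseline (preoperative) concentrations of ouabain".

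Section 3K describes the analysis differently: "Mean comparisons will be made by ANCOVA and, as appropriate, parametric or non-parametric tests". It adds "We will control for GFR and sex". Ouabain is not listed.

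The Rationale (section 2) presents pre-operative endogenous ouabain (EO) as a marker for kidney injury and describes a gradient: "the highest plasma EO concentrations are associated with the highest risk and poorest clinical outcomes".

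Under Enrollment and Baseline (3D), the blood samples for EO and the other biomarkers "will be drawn prior to investigational drug administration". The same section notes that ouabain results take many days and will not be available before surgery. Section 3E says "Stratified randomization will be employed using race and sex".

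**The concern.** Ouabain enters the primary analysis only as a filter: a patient is above the cut or not. Within the upper half, any remaining relation between ouabain and post-operative renal function goes into the residual variance. Because the result arrives after surgery, randomisation cannot be stratified on it. The analysis model is therefore the only place where the plan can use the information.

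At stake is precision in a primary test whose power, on the plan's own inputs, is below 80%. The two sections also disagree on whether the primary test has any covariates. If 3I governs, baseline GFR and sex are left out as well.

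**Working it through.** **Inputs.** Section 3L gives a creatinine difference of 36 µmol/l, an SD of 76 (for the post-operative creatinine increase) and 62 patients per group in the upper ouabain half. This fits 250 evaluable patients ÷ 2 halves ÷ 2 arms = 62.5. The significance level is not stated; two-sided 5% is assumed. Equal allocation is assumed, consistent with 62 per group.

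**Step 1: the plan's own figure.** The standard error of the difference is 76 × √(2/62) = 13.65. The noncentrality is 36/13.65 = 2.637, with 122 degrees of freedom. Noncentral-t power is 74.4% (75.1% by the normal approximation). The stated figure of more than 70% is reproduced.

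**Step 2: effect of restricting to the upper half.** If log ouabain is normally distributed (assumed), its variance above the median is the fraction v = 1 − 2/π = 0.363 of the full variance. A full-sample correlation R with the outcome then becomes, within the upper half,

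r² = R²v / (1 − R² + R²v).

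For R = 0.4: 0.16 × 0.363 / (1 − 0.16 + 0.0581) = 0.0581/0.8981 = 0.065.

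**Step 3: power with ouabain as a covariate.** The residual SD is 76 × √(1 − r²). The documents give no value of R, so the range is assumed.

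| Assumed full-sample R | Upper-half r | Variance removed (r²) | Residual SD | Power |
|---|---|---|---|---|
| none | 0 | 0% | 76.0 | 74.4% |
| 0.1 | 0.06 | 0.4% | 75.9 | 74.6% |
| 0.2 | 0.12 | 1.5% | 75.4 | 75.1% |
| 0.3 | 0.19 | 3.5% | 74.7 | 75.9% |
| 0.4 | 0.25 | 6.5% | 73.5 | 77.2% |
| 0.5 | 0.33 | 10.8% | 71.8 | 79.1% |

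Losing one degree of freedom changes these figures by about 0.01 percentage points. At R = 0.4 the gain is worth 62/(1 − 0.065) = 66.3 patients per arm, about 4 more than planned.

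**Step 4: if DigiFab flattens the slope.** Suppose ouabain has slope b on placebo and 0 on DigiFab. A common-slope model fits b/2. Averaged over the arms, the ouabain contribution falls from b²/2 to b²/4 (in units of ouabain variance), so b²/4 is removed. With equal slopes b² would be removed, so a quarter of the reduction remains. At R = 0.4 that is 6.5%/4 = 1.6%, which gives a residual SD of 75.4 and power of 75.1%, a gain of 0.7 points.

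**Limits.** The inputs are on the creatinine scale, while the endpoint is change in GFR. Section 3L does not say that the SD of 76 is adjusted for baseline GFR or sex. Only the part of ouabain's correlation that remains after those covariates would count, so overlap with baseline GFR lowers every row.

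**The case against.** The strongest reply is that nothing here is an error. Leaving out a prognostic covariate does not bias a randomised comparison, and the plan may choose its covariates. That stands. A reader might infer that chance imbalance in ouabain is a second harm on top of lost precision. It is not. With 62 per arm, a one-standard-error imbalance is √(2/62) = 0.18 SD of ouabain. At R = 0.4 it shifts the estimate by 0.18 × 0.254 × 76 ≈ 3.5 µmol/l. The ouabain share of the sampling variance gives the same number: √(13.65² × 0.0647) ≈ 3.5. The standard error already contains it.

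A reader might also take ouabain to be a strong predictor within the primary set. The Rationale supports a gradient in risk, but it gives no correlation with GFR change, no gradient within the upper half, and no association after allowing for baseline GFR. A large gain is therefore unsupported. To reach 81% power, ouabain would have to explain 15% of the variance in the upper half. By the formula in Step 2 that needs a full-sample correlation of about 0.57, or 33% of full-sample variance. The restriction to the upper half already removes most of what the covariate could offer.

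Finally, the plan's own hypothesis, that DigiFab neutralises ouabain, predicts a flatter slope in the treated arm, which shrinks the gain further. That also stands.

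What the reply does not remove is that the value will exist for every patient in the primary set, is a valid pre-treatment covariate, and costs one degree of freedom. Nor does it settle whether 3I or 3K defines the primary test.

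**Conclusion.** The point holds as an efficiency improvement, not as a flaw that threatens validity. Neither section adjusts for baseline ouabain, and they differ on whether there is any adjustment. The likely benefit is small: on the plan's inputs, 0.2 to 4.7 percentage points of power for assumed full-sample correlations of 0.1 to 0.5, and no more than 2.8 points at 0.4 or below. Even at 0.5 power stays just under 80%. These figures rest on an assumed two-sided 5% level, equal allocation, normally distributed log ouabain, a common slope in both arms, and no overlap with baseline GFR; failure of either of the last two lowers the gain. The omission itself is certain from the text; the size of the gain is not.

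**What to change.** In both 3I and 3K, name the same primary analysis: an ANCOVA of change in GFR in the high-ouabain half, with arm, baseline GFR, sex and log baseline ouabain as a continuous covariate. Remove the ANOVA wording from 3I; editing 3K alone would leave an analysis without covariates standing as the primary one. Fix the model before unblinding, because a covariate added later would look data-driven.

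The cost is a line or two of wording in each section and one degree of freedom for the ouabain term. No extra sample or measurement is needed.
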